[figure not shown]
[figure not shown]

Fig. 2: Computational model of (a) the bones and muscles, (b) the entire upper arm of the subject 1.

correlation with the intramuscular EMG signals. The decomposed 128-channel surface EMG monopolar action potentials and the bipolar action potentials of the MU3 and MU6 in Subject 1 are presented in Fig. 3 as an example.

Source model: Considering the irregular and arbitrary shape of muscle fibers in human body, a distributed source model, which has the capability of accurately describing bioelectric activity without prior assumptions about its shape, was employed in the proposed 3DIZI (Zhang et al. 2006; Zhang et al. 2008; Zhang et al. 2010; Liu et al. 2015). Specifically a total number of 72,840 current dipoles were evenly distributed in the 3D space of the biceps with a spatial resolution of $2 \times 2 \times 2 \text{ mm}^3$, and each dipole has three orthogonal components that need to be determined.

3DIZI Inverse Solution: The linear relationship between the source space and measurement space is

$$L \cdot X = \Phi \quad (1)$$

where $\Phi = (\phi_1, \phi_2, \dots, \phi_M)^T$ is the vector of surface EMG measurements, $X = (x_1, x_2, \dots, x_{3 \times N})^T$ is the vector representing the strength of the distributed dipoles in the 3-dimensional space of the biceps,

$L = (L_1, L_2, \dots, L_N)$ is the transfer matrix and L_i is an $M \times 3$ matrix that represents the electric lead field of the i -th dipole. M refers to the number of surface recording electrodes over the skin and N refers to the number of dipole sources in the source space. The transfer matrix L can be calculated by solving the forward problem (Zhang et al. 2004). The weighted minimum-norm (WMN) regularization technique (Zhang et al. 2008; Zhang et al. 2010) was employed to solve the inverse problem and the electrical activities can be estimated as follow (Fuchs et al. 1999).

$$\hat{X} = (R^T W^T W R)^{-1} L^T (L (R^T W^T W R)^{-1} L^T + \lambda I)^{-1} \Phi \quad (2)$$

where W is a $3N \times 3N$ weighted matrix which accounts for the undesired depth dependence, λ is the regularization parameter which is determined by means of the L -curve method (Hansen 1992), R is the source covariance matrix, which is constructed by taking the advantage of the surface location of the IZ identified from the corresponding bipolar MUAP trains, to constrain the muscle activity imaging solution in 3DIZI to improve its localization accuracy.

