The surface position of the IZ of a particular MU can be identified from the bipolar map of the decomposed high-density MUAPs by checking the phases of the propagating signals. A cylinder with the diameter of 20 mm (Buchthal and Sten-Knudsen 1959; Merletti et al. 1999) is defined right underneath the identified surface IZ location and axially pointed to the normal direction of the skin surface, and the cylinder will create a cylindrical shaped sub-space in the target muscle space. A high weighting factor

(0.9) is applied to the cylindrical sub-space and a low weighting factor (0.1) is applied to the rest 3D muscle space, and the source covariance matrix R in Equation (2) is then calculated accordingly.

Evaluation of the 3DIZI in computer simulations

A series of computer simulations were conducted based on the FE model of the upper arm in Fig. 1 to evaluate and optimize the performance of the 3DIZI approach in localizing IZs in the 3D space of the biceps. One extended activation zone in an ellipsoidal shape with semi-axes length of 5 and 4 mm in parallel and normal to the muscle fiber directions were assumed in the biceps, with different depths (10, 15 and 20 mm depths from the skin surface) (Merletti et al. 1999; Merletti et al. 2008). At each depth, one activation zone was assumed at 6 locations in the biceps along the muscle fiber direction, or one pair of activation zones were assumed at 3 different locations which are symmetrical to the mid-axial plane the biceps. The electrical potentials at 128 EMG electrode locations were calculated based on the FE model as the simulated surface EMG measurements after adding Gaussian white noises at different noise levels (SNRs = ∞ , 30, 25, 20) (Phinyomark et al. 2012).

The localization error (LE) was employed to evaluate the accuracy of the 3DIZI results. The LE is defined as the spatial distance between the center of the assumed target activation zone and that of the reconstructed muscle activation zone. For the cases with two activation zones, the LE was calculated by averaging the two individual LEs. Fig. 4 presents the mean and standard deviation of LEs achieved at different noise levels and source depths. The noise and source depth does affect the accuracy of the 3DIZI results, but the all mean LEs are less than 5 mm for all the cases, which demonstrates the high performance of the 3DIZI.

[figure not shown]
[figure not shown]

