The purpose is to evaluate the performance of the 3DIZI approach in localizing IZs in the 3D space of the spastic muscles with simultaneous high-density surface EMG and intramuscular EMG recordings.

Eight patients with spastic biceps will be recruited to participate in this validation study in TIRR. The same protocol will be used as described in our preliminary study (Liu et al. 2015).

Simultaneous surface EMG and intramuscular EMG recordings: Simultaneous surface EMG and intramuscular EMG measurements will be acquired from the spastic biceps of the patients with a 136-channel Refa (TMSi, Enschede, The Netherlands). Patients will be seated comfortably on a height-adjustable chair. The arm to be tested will be secured firmly on a customized apparatus with the elbow joint at approximately 90 of flexion and the shoulder at approximately 45 of abduction and 30 of flexion. The 128-channel unipolar surface EMG signals will be recorded with 2 flexible 2-dimensional 64-channel (in 8x8 formation, individual recording probe 4.5 mm in diameter, center-to-center probe distance 8.5

mm) surface electrode array (TMSi, Enschede, The Netherlands). The skin of the tested muscle will be carefully prepared, and the electrode array was attached to the biceps muscles with a double adhesive sticker and further secured with medical tapes. A coating fine wire electrode (VIASYS Healthcare, Madison, WI) will be inserted into the mid-axial section of the biceps to record bipolar intramuscular EMG signals. Ultrasound scan (M Turbo, SonoSite, Bothell, WA) will be performed on the biceps to identify the location of the inserted wire electrode. Patients will be asked to contract their impaired biceps to perform maximum voluntary contraction (MVC) of elbow flexion against the vertical plates 3 times. Each trial will last for 10 sec. A sampling rate of 2 KHz will be used for simultaneous surface and intramuscular EMG recordings during muscle contraction.

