injection. Ultrasound guidance can help ensure depth of needle tip location, i.e., to make sure the needle tip is within the muscle, but it is not able to tell where it is located with reference to the IZs of the entire muscle. However, in the IZ-guided injection technique, IZ location obtained using the 3DIZ will be first marked over the skin surface of the muscle and the depth of the IZ will be also provided. The 3DIZ as described in Aim 1 will be applied to the IZ-guided injection group 1 day prior to scheduled injection. The surface location and depth information of the IZ will be used to guide where the needle tip needs to go. Currently, patients commonly receive 1 to 2 injection sites, occasionally 3 sites for biceps muscles. To standardize the procedure, we will choose 2 sites for all patients.

Treatment outcome evaluation and comparison: Treatment outcomes include clinical assessment of spasticity (MAS scale, see Human Subject Protection section) and quantitative assessment. Standard physical therapy will be ordered to both groups as part of standard of care for patients after BTX injections to maximize the outcomes. For quantitative assessment, we will adopt the same protocol in our recent study which quantified elbow flexors spasticity by measuring reflex torque (Figure 6)(Bhadane et al. 2015).

Fig. 6: Experimental setting (upper) and representative data (lower).

Each subject will receive a total of 60 degrees of computer-controlled elbow extension stretching at different speeds. The stretch ends at 10 degrees beyond the resting angle of the elbow joint during standing to offset the baseline difference among subjects (Bhadane et al. 2015). From the angle-torque relations, reflex torque is obtained after subtracting passive torque at 5°/sec from those at 50°/sec or 100°/sec. reflex torque is considered to reflect neural component of muscle spasticity (Kamper et al. 2001; Kamper et al. 2003; Li et al. 2006). It is expected to be reduced with spasticity reduction after neuromuscular blockade by Botox.

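### Equation (2) and the 0.9/0.1 definition of R are inconsistent: any R that rises with the stated weights disfavours the cylinder it is meant to favour

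*Combined protocol and SAP*

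**What the plan says.** Section 3, Preliminary results, 3DIZI Inverse Solution, gives the estimator as Equation (2). In plain notation it reads X = (R'W'WR)^-1 L' [L (R'W'WR)^-1 L' + λI]^-1 Φ, where W corrects for depth and λ is the regularisation parameter. The text then defines R: "R is the source covariance matrix, which is constructed by taking the advantage of the surface location of the IZ". The stated purpose is to constrain the imaging solution and so improve localisation.

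The next paragraph builds R. A cylinder 20 mm in diameter is placed under the surface IZ. A high factor of 0.9 "is applied to the cylindrical sub-space and a low weighting factor (0.1) is applied to the rest 3D muscle space". The paragraph ends by saying only that R follows from these weights; the step from the weights to the entries of R is not written out.

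The trial reuses the method. For Experiment 1 (Section 4), "The same protocol will be used as described in our preliminary study", and its validation steps reconstruct muscle activity with 3DIZI. For Experiment 2 (Section 4, BTX injections), the method is applied one day before injection in the IZ-guided group, and "The surface location and depth information of the IZ will be used to guide where the needle tip needs to go".

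**The concern.** In an estimator of this form, the matrix on either side of the lead field is the prior covariance of the sources. A large entry lets a dipole be active; a small entry suppresses it. Equation (2) uses the inverse of R'W'WR in that place, so a large entry of R suppresses the dipole. The text calls R a covariance and gives the larger factor to the region it wants to favour. The name, the weights and the purpose all point one way, and the formula points the other.

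There are two possibilities, and both need action. If the code follows the printed formula, the reconstruction works against its own prior, and Experiment 1 would validate, and Experiment 2 would use, that reconstruction. If the code is right, the document misstates the method, and a reader who implements it as printed gets the reverse of what was intended.

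**Working it through.** The documents give no penalty ratio or prior variance ratio, so there is no stated figure to reproduce. The check is algebra on Equation (2) with the two weights.

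**Inputs.** The weights are 0.9 inside the cylinder and 0.1 outside, and Equation (2) is as printed (both Section 3). Assumptions: R and W are diagonal, and the two dipoles compared have the same depth weight w, so that W cancels.

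**Step 1: what Equation (2) minimises.** Write A = R'W'WR and C = A^-1. By the standard matrix identity,

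C L'(L C L' + λI)^-1 Φ = (L'L + λA)^-1 L'Φ.

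The right-hand side minimises ||Φ − LX||² + λ||WRX||². The penalty on dipole i is therefore proportional to (w r_i)², and its prior variance to 1/(w r_i)².

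**Step 2: the plain reading, R = diag(0.9, 0.1).**
- Inside: penalty 0.9² = 0.81; prior variance 1/0.81 = 1.23.
- Outside: penalty 0.1² = 0.01; prior variance 1/0.01 = 100.
- Prior variance, inside to outside: 0.01/0.81 = 0.0123 = 1/81.

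**Step 3: other mappings from weight to R, put into Equation (2) as printed.**

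| Entries of R | Prior variance, inside : outside | Cylinder |
|---|---|---|
| square root of weight | 0.1 : 0.9 = 1 : 9 | disfavoured |
| weight | 0.01 : 0.81 = 1 : 81 | disfavoured |
| square of weight | 0.0001 : 0.6561 = 1 : 6561 | disfavoured |
| 1/weight | 0.81 : 0.01 = 81 : 1 | favoured |

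Because prior variance falls as r_i rises, every mapping that increases with the weight disfavours the cylinder. Only an inverse-type R favours it, and an R that is smaller where sources are expected is not a source covariance.

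**Step 4: what a consistent formula would give.** If 0.9 and 0.1 are entries of a covariance R, then C = R^(1/2)(W'W)^-1 R^(1/2)' gives 0.9 : 0.1 = 9 : 1 in favour of the cylinder. If they are amplitude weights, C = R(W'W)^-1R' gives 0.81 : 0.01 = 81 : 1. The documents do not say which is meant.

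**The case against.** The strongest reply is that this is a slip of notation in a description of pilot work. The pilot evaluation in healthy subjects reports that, in Subject 1, where the wire electrode lay in the IZs of the analysed motor units, the reconstructed zones and their overlap covered the wire. That is hard to square with a solution pushed out of the region under the surface IZ, so the code may well be right. Further, R is only said to be calculated in line with the weights, the Experiment 1 text points to the pilot publication, which may define R properly, and an inverse sign on R could have been lost when the PDF was read.

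Much of this stands. A reader might infer that needles will be guided by a reversed solution. The documents do not support that, because they do not show that the software follows the printed form. Nor do they fix 81 as the size of the penalty, or 81:1 as the intended ratio. The reach is also limited: the surface IZ is read from the bipolar map before Equation (2) is applied, so depth is the needle input that most clearly depends on the inverse solution.

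It does not remove the inconsistency. The same term is printed twice in Equation (2), without an inverse on R in either place. No other inverse rule appears in the document. The coverage result comes from two subjects, and the motor-unit labels are swapped between the decomposition paragraph (units 3 and 6 in Subject 1, units 1 and 5 in Subject 2) and the evaluation paragraph (the reverse), so it cannot settle the matter alone. The small simulated localisation errors cannot settle it either: they are distances between centres, and activity displaced evenly around a cylinder can still have its centre inside it.

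**Conclusion.** The inconsistency holds. As printed, Equation (2) penalises whatever R makes large, so any R that rises with the 0.9/0.1 weights works against the stated aim. The direction depends only on the form of the equation and on R increasing with the weight. The size does not have that standing: 1/81 assumes R = diag(0.9, 0.1), diagonal W and equal depth weight, and the other increasing mappings tried run from 1/9 to 1/6561.

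This is a fault in the specification. Whether it is also a fault in the computation is open, and the pilot coverage result leans against it. It deserves correction rather than a footnote because it is the only statement of the inverse solution on which the Experiment 1 validation and the Experiment 2 needle guidance both rest.

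**What to change.** 1. State how the weights define R.
2. Correct Equation (2) so that a higher weight gives a larger prior source variance. If the weights are covariance entries, use for example C = R^(1/2)(W'W)^-1 R^(1/2)' in place of (R'W'WR)^-1. If they are amplitude weights, use C = R(W'W)^-1R' and do not call R the covariance.
3. Confirm which form the trial code uses. Before the first guided injection, rerun one existing simulated case with that code and confirm that reconstructed energy concentrates in the cylinder. Report this alongside the localisation error, since a centre distance alone may not show the direction of the weighting.

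The cost is one corrected formula with its definition and one rerun of an existing simulation. Patients, visits and sample size are unaffected.

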Simultaneous surface EMG and intramuscular EMG measurements were acquired from the biceps of the two healthy male subjects with a 136-channel Refa (TMSi, Enschede, The Netherlands). The 128 unipolar channels were employed for surface EMG measurements and one bipolar channel was employed for simultaneous intramuscular EMG measurements for the validation purpose (Fig. 1(a)). A sampling rate of 2 KHz was adopted for both surface and intramuscular EMG recordings. The depth of the wire electrode inserted in the biceps was characterized (green circle) from the ultrasound images (Fig. 2(b)).

Computational model of the upper arm:

A computational upper arm model was constructed from a general MR image data set and modified to match the ultrasound images of the subject's upper arm. The model consists of the skin, fat, biceps, triceps, compact bone and cancellous bone and was meshed with ANSYS 13.0 (ANSYS, Canonsburg, PA) into a finite element (FE) model for computation (Fig. 2). The entire FE model of the upper arm consists of 225,462 tetrahedron elements and 39,605 nodes. The conductivity values assigned to the skin, fat, muscle, compact bone and cancellous bone are 4.55×10^{-4} S/m, 0.0379 S/m, 0.2455 S/m, 0.02 S/m and 0.075 S/m, respectively (Lowery et al. 2002). An anisotropy ratio (longitudinal/transverse conductivities) of 5 was assumed for the biceps muscles in the model (Stoykov et al. 2005).

Surface EMG Decomposition:

The K-means clustering and Convolution Kernel Compensation method (KmCKC) which we newly developed (Ning et al. 2015) was employed to decompose the 128-channel surface EMG signals into their constituent MUAP trains. The correlation between each decomposed MUAP train and the simultaneously recorded intramuscular EMG signals was calculated. A high correlation indicates that the corresponding MUAP train and the simultaneously recorded intramuscular EMG signals were generated by the same MU. The correlation calculation results showed that the 3rd and 6th MUAP trains in Subject 1 and the 1st and 5th MUAP trains in Subject 2 have the significantly high

[figure not shown]

Fig.1: shows (a) positions of 128-channel surface EMG recording electrodes (2 flexible 8 × 8 arrays with the electrode diameter of 4.5 mm, and the center-to-center electrode distance of 8.5 mm) and wire electrode (green star) over the subject's right upper arm, and (b) location of the inserted wire electrode (green circle) in the ultrasound image of the upper arm.

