Validation: 1) The recorded 128-channel surface EMG signals will be first decomposed into their constituent MUAP trains using the KmCKC approach (Ning et al. 2015); 2) Correlations between each MUAP trains and the intramuscular EMG signals will be calculated to identify the MUs which were simultaneously recorded by both the surface EMG and wire EMG electrodes; 3) the muscle activities of the MUs, which were simultaneously recorded by both surface EMG and wire EMG electrodes, will be reconstructed in the 3D space of the biceps from their MUAPs respectively using the 3DIZI approach; 4) the localization error (LE), defined as the distance between the center of the reconstructed muscle activation zone or IZs and the location of the inserted wire electrode identified in ultrasound images, will be calculated. The mean value and standard deviation of LEs achieved from each patient will be calculated to evaluate the accuracy of the 3DIZI results.

Pitfalls: Attempts will be made to insert the wire electrode into IZs in the mid-axial section of the biceps so that muscle activities in IZs can be recorded. However, it is possible that the wire electrode will not be inserted into any IZ of the specific biceps and no muscle activities in IZs can be measured. In this case, the propagating muscle activities measured by the wire electrode, as demonstrated in Fig. 5(a2) - (c2) will be used to evaluate the proposed 3DIZI approach. For patients who cannot contract their spastic biceps efficiently, electrical stimulation will be delivered to the musculocutaneous nerve using an electrical stimulator (D7SA, Digitimer Ltd, Hertfordshire, England) to generate a maximum response. Techniques for removal of stimulation artifacts have been recently developed by our group (Li et al. 2014).

Experiment 2: Evaluation of the feasibility of utilizing the 3DIZI to optimize the BTX injection

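### Experiment 1 describes no masking to the wire position and no locking of the 3DIZI result before the localization error is computed, so analyst choices could lower that error

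*Combined protocol and SAP*

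**What the plan says.** Section 4, Experiment 1, sets out the validation in four steps: decompose the surface EMG, use correlation with the wire signal to pick the motor units that both systems recorded, reconstruct those units with 3DIZI, and compute LE. LE is the distance between "the center of the reconstructed muscle activation zone or IZs and the location of the inserted wire electrode identified in ultrasound images". The mean and SD of LE per patient are the only summaries named. No acceptance limit is set.

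The reference comes from the recording session: "Ultrasound scan (M Turbo, SonoSite, Bothell, WA) will be performed on the biceps to identify the location of the inserted wire electrode". Section 6 says that data are saved for off-line analysis. Neither section says who reads the wire position, when it is read, or whether the person running 3DIZI sees it.

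Most of the method comes from the pilot, because in Experiment 1 "The same protocol will be used as described in our preliminary study". In the pilot description (section 3, Preliminary results):

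- The surface position of a unit's IZ "can be identified from the bipolar map of the decomposed high-density MUAPs by checking the phases of the propagating signals".
- A 20 mm cylinder is placed under that position and weighted 0.9, against 0.1 for the rest of the muscle.
- The regularisation parameter is set by the L-curve method.
- "A computational upper arm model was constructed from a general MR image data set and modified to match the ultrasound images" of the subject's arm. The Fig. 1 legend describes panel (b) as the "location of the inserted wire electrode (green circle) in the ultrasound image of the upper arm".

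If the wire misses every IZ, the Pitfalls paragraph of Experiment 1 falls back on propagating activity.

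**The concern.** In an accuracy study, the person producing the test result should not know the reference result while judgement is still being used. Here the scan that shows the wire precedes the reconstruction, and several steps of the reconstruction have no written rule. Section 3 presents 3DIZI as the study group's own method, and the plan names nobody outside that group to apply it.

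Where two or three readings of a map are equally defensible, knowing the wire position can tip the choice towards the one that lands nearer. LE would then look better with no gain in accuracy. LE is the only defined result of Experiment 1 and has no acceptance limit, so any accuracy claim for spastic muscle would rest on the raw mean. Section 3 says why millimetres count: it cites a 46% loss of toxin effect for 1 cm of added distance from the IZ.

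**Working it through.** **1. Search for a safeguard.** The protocol contains no statement on masking, independent reading or locking of results for Experiment 1. The Validation paragraph does place reconstruction (step 3) before the comparison with the wire (step 4). That orders the calculations. It does not order who knows what.

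**2. Sort the settings.**

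| Setting | Where | Rule stated? |
|---|---|---|
| Decomposition algorithm | Exp. 1, Validation | Yes, named |
| Cylinder diameter, 20 mm | Sec. 3, inverse solution | Yes |
| Weights 0.9 / 0.1 | Sec. 3, inverse solution | Yes |
| Regularisation parameter | Sec. 3, inverse solution | Yes, L-curve |
| Correlation cut-off for units | Exp. 1, Validation | No |
| Surface IZ reading | Sec. 3, inverse solution | Principle only; no algorithm or reader |
| Zone extent and centre | Exp. 1, Validation | No |
| Time instant in the fallback | Exp. 1, Pitfalls | No |

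The surface IZ reading matters most. It places the cylinder, whose weight is 0.9/0.1 = 9 times that of the rest of the muscle.

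The time instant can also move the result. At the planned 2 kHz, one sample shifts a propagating zone by 1000·v/2000 mm, where v is conduction velocity in m/s. For an assumed v of 3 to 5 m/s (not in the documents), that is 1.5 to 2.5 mm per sample.

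**3. Illustrate the size.** The plan gives no patient LE, target or SD, so there is no figure of its own to reproduce. Assumptions: the 3-D error is normal and equal on each axis; the true mean LE is 5 mm; k candidate reconstructions have errors with correlation ρ; and the one nearest the wire is always kept. The 5 mm is a scale borrowed from the pilot's computer simulations, where all mean LEs were below 5 mm.

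The mean distance for per-axis SD s is 2s√(2/π), so s = 5/1.596 = 3.13 mm. The mean of the smallest of k distances, by Monte Carlo, is:

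| ρ | k = 2: mean LE (reduction) | k = 3: mean LE (reduction) |
|---|---|---|
| 0 | 3.81 mm (24%) | 3.27 mm (35%) |
| 0.5 | 3.96 mm (21%) | 3.47 mm (31%) |
| 0.8 | 4.26 mm (15%) | 3.91 mm (22%) |
| 0.9 | 4.46 mm (11%) | 4.20 mm (16%) |
| 0.95 | 4.62 mm (8%) | 4.42 mm (12%) |

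Reduction is (5 − mean LE)/5; for example, (5 − 3.81)/5 = 24%.

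If the candidates differ on one axis only, such as depth, correlations of 0.5 to 0.8 on that axis give reductions of 7–11% for k = 2 and 10–14% for k = 3.

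**The case against.** **The plan is silent; it does not rule masking out.** This stands. A reader might infer that nobody will be masked. The documents do not say so: Experiment 1 takes its procedure from a pilot paper that is not reproduced in full, and the protocol does not say when the wire coordinates are read. The supportable statement is that no masking or locking is described.

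**The ultrasound-fitted arm model makes the test circular.** A reader might infer this too, and it does not hold. Fitting skin, fat, muscle and bone to a subject's ultrasound is anatomical personalisation and does not by itself pull the solution towards the wire. Nor does the text say that the same frames serve both purposes. What remains is narrower: the pilot's ultrasound image showed the wire, so the person fitting the model may see it.

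**Much is already fixed.** This stands for the algorithm, cylinder, weights and L-curve. For a wire inside an IZ, the pilot text also ties the relevant instant to the start of the action potential in the IZ. The freedom left is the set of unstated rules in the table above. Using the wire signal to choose units is inherent in the design; the gap there is the missing cut-off.

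**LE may be too high, not too low.** LE runs from the zone centre, and the wire need not sit at the centre. The simulated zones had semi-axes of 5 and 4 mm, so a perfect image could still score several mm. This stands as a reason not to call the overall direction proven. It does not remove the selection effect, because that offset is present with or without masking.

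**The percentages are a worst case.** They assume that the nearest candidate is kept every time. Candidates built from the same data, model and cylinder may be highly correlated, which favours the lower rows of the table.

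**A biased LE would mis-steer the injections.** A reader might infer this, but the plan does not support it. No wire is described in Experiment 2, LE does not enter needle placement, and no LE value decides whether Experiment 2 proceeds.

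**Conclusion.** The concern holds in a limited form. Experiment 1 describes neither masking to the wire position nor locking of the 3DIZI result before LE is computed, and four influential choices have no full written rule. If those choices are made with the wire position in view, LE may be understated. Whether that will happen, and by how much, cannot be derived from the documents.

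The illustrative reductions of about 15–35% (correlations 0 to 0.8) and 8–16% (0.9 to 0.95) rest on an assumed 5 mm true mean LE, equal error on each axis, two or three candidates, and selection of the nearest every time. They show what full selection could do and are not a forecast. What is at stake is the credibility of Experiment 1's accuracy figure. The point does not touch the conduct of Experiment 2 or the sample size. It is worth acting on because the remedy is cheap and cannot be applied after reconstructions have been made with the answer visible.

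**What to change.** In the Validation paragraph of Experiment 1, insert a requirement before step 4:

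1. The analyst selects motor units from the wire signal, using a correlation cut-off set in advance, and does not use the wire's ultrasound position.
2. The rules for reading the surface IZ, for the zone's extent and centre, and for the time instant in the fallback case are written down before the first reconstruction. The cylinder, weights and L-curve rule are confirmed as carried over from the pilot.
3. For each unit, the surface IZ, time instant, regularisation value and 3DIZI centre are recorded in a dated, locked file.
4. Only then are the wire coordinates read or released, and LE computed.

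For the arm model, use ultrasound frames that do not show the wire, or hide it in the frames used.

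The cost is a small change in workflow and some record-keeping. Because the scan can be stored and read later, no extra patients, staff or procedures are needed. Masking will be partial, since the plan places the wire in the mid-axial section and the analyst will know that. The exact position and depth can still be withheld.
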